4.2 STUDY DESIGN

This is a prospective, multi-center, open-label, single arm study to evaluate the safety and technical performance of the CathVision ECGenius® system in up to 30 adult patients scheduled to undergo an EP procedure.

Intracardiac signals will be passively recorded in parallel with the commercial EP recording system. The tested device will not be used to direct clinical care decisions or therapy. The EP procedure will be guided by study site's standards of care. A summary of the schedules of evaluations and visits can be found in section 4.7.1.

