4.5 STUDY OUTCOMES

4.5.1 PRIMARY OUTCOME

The Primary endpoint of the study will be evaluated as the technical success of CathVision ECGenius® System to collect and record intracardiac signals during routine EP procedures. Specifically:

- To record and plot low voltage electrograms
- To assess the improved signal (better signal to noise ratio) compared with the standard signal
- To visualize the shape and timing of electrograms

A defined evaluation scale for CathVision ECGenius signal versus the standard of care signal will be defined as 1 (best) to 5 (worse) for different areas of interest. This evaluation will be done by the institution principal investigator for both signal and mapping if available.

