7.2 DESCRIPTIVE ANALYSES

Continuous variables will be summarized using standard quantitative statistics: number of available observations, mean, standard deviation, median, quartiles, and range (minimum and maximum observed values). The number of missing observations, if any, will also be summarized.

Categorical variables will be summarized using classical frequency statistics: number of non-missing observations and percentages by categories. Number and percent of missing data, if any, will also be summarized.

There are no predefined criteria for terminating the study based on statistical outcomes. Missing data will not be replaced or imputed.

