## 5.4. Primary performance endpoints

The Primary Performance endpoint of study will be evaluated as technical success of CathVision ECGenius™ System to collect and record intracardiac signals during EP procedures. With focus on:

- To record and plot low voltage electrograms
- To assess the improved signal (better signal to noise ratio) compared with the standard signal
- To visualize the shape and timing of electrograms

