## 5.6. Statistical analysis

Endpoint	Statistical method	Hypothesis & benchmark
Freedom from major adverse events, evaluated at hospital discharge.	
 
• Count number of AEs
 
• Percentage: [Procedures with AE] / [Total number of procedures]
 
	
 
• 3.5% of patients develop major AE within 30 days of procedure.
 
• Zero CathVision Cube-related AE are expected.
 

Recording low-voltage electrograms	
 
• Count number of low-voltage electrograms plotted in total
 
• Percentage: [Total number low-voltage electrogram plots] / [Total number of procedures]
 
• Physician user quantitatively score low-voltage electrogram plots on “ease” of interpretation of EGMs” [0-5] on CathVision Cube and on existing EP system 
 
○ 0: Impossible
 
○ 1: Very difficult
 
 
 
	
 
• At least one low-voltage electrogram plot per procedure
 
• CathVision not inferior to existing EP recording system
 

Document no.:	Effective Date:	Version: 1
Author: [name]	Approver:	Reviewer:

Endpoint	Statistical method	Hypothesis & benchmark
	
 
 2: Difficult
 
 3: Possible
 
 4: Easy
 
 5: Very easy
 
 
 
• Average physician score on CathVision ECGenius™ vs average physician score on existing EP system
 
	
Assessing the improved signal quality (baseline noise level peak-to-peak)	
 
• Peak-to-peak amplitude of baseline noise, on unipolar electrogram, at at least 1 site with low-voltage electrograms, and averaged if more than 1.
 
• Peak-to-peak amplitude of baseline noise, on bipolar electrogram, at at least 1 site with low-voltage electrograms, and averaged if more than 1.
 
• Non-inferior peak-to-peak amplitude of baseline noise to existing EP recording system.
 
	
 
• Hypothesis is below 50uV unipolar baseline noise peak-to-peak
 
• Hypothesis is below 20uV bipolar baseline noise peak-to-peak
 
• Hypothesis is non-inferior to existing EP recording system.
 

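### SAP 5.6 lists non-inferiority for physician score and baseline noise but gives no margin, confidence interval or decision rule, so the conclusion would exclude no deficit.

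*SAP*

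**What the plan says.** SAP 5.4 states: "The Primary Performance endpoint of study will be evaluated as technical success". It lists three areas of focus, and SAP 5.6 gives each a row with a method and a hypothesis or benchmark.

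- **Physician score (low-voltage electrogram row).** A physician scores ease of interpretation from 0 (impossible) to 5 (very easy) on both systems. The comparison is "Average physician score on CathVision ECGenius™ vs average physician score on existing EP system" and the benchmark is "CathVision not inferior to existing EP recording system".
- **Baseline noise (signal quality row).** Unipolar and bipolar noise are measured at one or more low-voltage sites and averaged over sites. The device has absolute targets of 50 µV and 20 µV. The line in the method column that names the comparator reads "Non-inferior peak-to-peak amplitude of baseline noise to existing EP recording system", and the next column repeats this as a hypothesis.
- **Shape and timing.** Only this row is marked as exploratory, with no hypothesis.

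Protocol 4.2 makes the data paired: "Intracardiac signals will be passively recorded in parallel with the commercial EP recording system". Protocol 7.1 says that no formal hypothesis was used to derive the sample size. Protocol 7.2 lists descriptive statistics only and says of missing data: "The number of missing observations, if any, will also be summarized" and "Missing data will not be replaced or imputed". Protocol 4.1 and the SAP synopsis place benchmarking of signal quality under the secondary objective. Protocol 4.5.1 describes a rating of the two signals that "will be defined as 1 (best) to 5 (worse) for different areas of interest".

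**The concern.** A non-inferiority statement means that a deficit of a named size has been ruled out. SAP 5.6 names no size and plans no interval that could rule one out. A report that follows the SAP could therefore call ECGenius not inferior, under a primary performance endpoint, because two averages looked similar.

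The criterion is also open. The wording could mean that the observed average is no worse, or that it is not significantly worse. These readings behave very differently, and nothing prevents the choice being made after the data are seen.

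Two smaller gaps affect the same comparison. The SAP does not say whether several scores from one procedure are averaged before systems are compared, although it does average noise over sites. The scale in Protocol 4.5.1 also runs the opposite way to the one in SAP 5.6, and neither document explains how they relate.

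**Working it through.** **Inputs from the documents.** Up to 30 subjects (Protocol 4.2 and 4.4); both systems recorded in the same procedure (Protocol 4.2); some screen failures use up places under the cap (Protocol 4.7.3). **Assumed, because the documents give no value:** the SD of the within-procedure differences (shown as a range), 95% two-sided intervals, and independent procedures.

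**1. The plan's own figure.** SAP 5.5 takes 30 as the average of three trials: (30 + 20 + 40)/3 = 30. This reproduces, but it has no link to a margin, an SD or power.

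**2. Is the estimate itself wrong?** No. With complete pairs, mean(ECGenius) − mean(existing) = mean(ECGenius − existing). The two forms differ only if some procedures contribute to one average and not the other.

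**3. Uncertainty left out.** Half-width = t(0.975, n−1) × SD/√n.

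- n = 30: 2.045/5.477 = 0.373 SD.
- n = 25 (illustrating five lost pairs): 2.064/5 = 0.413 SD.

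| Measure | Assumed SD of differences | Half-width, 30 pairs |
|---|---|---|
| Score (points) | 0.5 / 1.0 / 1.5 | 0.19 / 0.37 / 0.56 |
| Unipolar noise (µV) | 5 / 10 / 20 | 1.9 / 3.7 / 7.5 |
| Bipolar noise (µV) | 2 / 4 / 8 | 0.7 / 1.5 / 3.0 |

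With 25 pairs the score half-widths become 0.21, 0.41 and 0.62. An observed difference of zero is compatible with a true deficit of the size shown.

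**4. How much the missing rule matters.** Suppose ECGenius is truly worse by 0.2 SD of the differences, with 30 pairs.

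- Reading A, observed average no worse: Φ(−0.2 × √30) = Φ(−1.095) = 0.14.
- Reading B, not significantly worse at two-sided 0.05: P(T < 2.045), with T noncentral t on 29 df and noncentrality 1.095, = 0.82.

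The same device passes 14% or 82% of the time, depending on a choice that the SAP leaves open. If the systems are truly equal, Reading A passes only 50% of the time.

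**5. What 30 pairs could support if a margin were set.** With true difference 0, one-sided 2.5% and 80% power, the smallest margin that can be excluded is 0.529 SD by the noncentral t. That is 0.26, 0.53 or 0.79 points for SD 0.5, 1.0 or 1.5. This matters only if the non-inferiority wording is kept.

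**6. The two scales.** Protocol 4.5.1 has the institution's principal investigator rate several areas, with 1 as the best value. SAP 5.6 has a physician user rate ease of interpretation, with 5 as the best value. Either the documents conflict or they describe two instruments. In the second case SAP 5.6 contains no analysis of the Protocol 4.5.1 rating.

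**The case against.** The strongest reply is that the study is descriptive. Protocol 7.1 and 7.2 point that way, the SAP column mixes hypotheses with plain expectations, benchmarking is a secondary objective, and the device does not direct care. This limits the seriousness of the point. It does not remove it: the noise row uses the word hypothesis, only the shape and timing row is set apart as exploratory, and SAP 5.4 places signal comparison under the primary performance endpoint. If description is what is meant, the non-inferiority wording should go.

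The 50 µV and 20 µV figures might be offered as margins. They are absolute targets for the device; non-inferiority to the existing system is listed separately.

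A reader might infer several stronger criticisms that the documents do not support:

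- **That comparing averages is a faulty estimate.** Step 2 shows that with complete pairs it is not.
- **That the noise row has no method at all.** The measurement and its averaging over sites are defined; only the rule for comparing systems is absent.
- **That failed recordings would go unseen.** Loss of waveform and interrupted recording are reportable under Protocol 6.6, malfunctions are a secondary endpoint in Protocol 4.5.2, and the SAP counts low-voltage plots against all procedures. What remains unstated is how such procedures enter the score and noise averages. Any resulting bias is only a possibility.
- **That the direction of the score comparison is unknown.** Within SAP 5.6 it is clear: higher is easier. The difficulty lies between the two documents.

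**Conclusion.** The point holds in a limited form and should be corrected before the data are analysed. As written, SAP 5.6 allows a non-inferiority conclusion for score and noise that its analysis cannot support, because no margin, interval or rule is given. The planned point estimate is sound on complete pairs.

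The unstated uncertainty is 0.373 SD of the within-procedure differences at 30 pairs, and more if fewer pairs are usable. Its size in points or microvolts depends entirely on the assumed SDs. The t interval is approximate for a bounded ordinal score and for noise amplitudes, which cannot be negative. With at most two sites, the score interval describes the participating readers and not readers in general.

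It would go too far to say that the trial fails a formal non-inferiority test or is underpowered for one. No such test is specified, and the protocol says that its size was not derived from a hypothesis.

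**What to change.** 1. In SAP 5.6, average scores within each procedure for each system. Report the mean within-procedure difference, ECGenius minus existing system, with a 95% confidence interval, for score, unipolar noise and bipolar noise. Use complete pairs, which respects the no-imputation rule, and show beside each result how many procedures lacked a usable recording on each system.
2. Then choose one of two courses. Either delete the non-inferiority wording from both rows and report descriptively; or keep it only with a justified margin for each measure, fixed before data are seen, that the interval must exclude. For the score, the lower limit must lie above minus the margin; for noise, the upper limit must lie below the margin. The documents give no basis for a margin, so the sponsor would have to supply one.
3. Reconcile the scales in Protocol 4.5.1 and SAP 5.6. If they really are different instruments, say so, state which one feeds this comparison, and state how the Protocol 4.5.1 rating will be analysed. Calling them different only to avoid an amendment would not be valid.

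**Cost.** SAP wording and a little more analysis, with no extra patients or readers. The non-inferiority label may be lost. The interval is not among the statistics listed in Protocol 7.2, but it can be added in the SAP. A protocol amendment with IRB approval (Protocol 8.9) is needed only if Protocol 4.5.1 is edited.

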4.7.4 VISIT 2: DAY 0 (INDEX PROCEDURE THROUGH DISCHARGE)

During the index EP procedure, institutional standard of care is to be utilized to treat the subject.

When the subject is connected to the standard EP recording system, during manipulation of catheters or diagnostic tests, intracardiac signals will be recorded using the investigational device in parallel. The total procedure time is not expected to differ by adding the CathVision ECGenius® system to the EP system as the final comparison of data recorded from the Standard EP recording system and the tested device will occur post procedure.

Prior to discharge, the following will be documented:

- Adverse events (AE)
- CathVision ECGenius device malfunctions
- Protocol deviations

Subjects will be considered to have completed and exit the study after this visit.

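### The baseline-noise comparison has no rule for sites or windows and no masked reader, so the plan permits a choice that would bias it towards ECGenius

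*SAP*

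**What the plan says.** In the SAP 5.6 table, the signal-quality row takes peak-to-peak baseline noise on a unipolar and on a bipolar electrogram, each "at at least 1 site with low-voltage electrograms, and averaged if more than 1". Three hypotheses rest on these values: "Hypothesis is below 50uV unipolar baseline noise peak-to-peak", "Hypothesis is below 20uV bipolar baseline noise peak-to-peak", and a comparison described as "Non-inferior peak-to-peak amplitude of baseline noise to existing EP recording system".

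On how the values are obtained, neither document gives:
- an amplitude below which an electrogram counts as low-voltage;
- a rule for which sites are measured, or an upper number;
- the position or length of the baseline window;
- a statement that both systems are read at the same site, electrodes, window and filter settings;
- a named or masked reader for the noise measurement.

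Two passages set the context. Protocol 4.2 states: "This is a prospective, multi-center, open-label, single arm study". Protocol 4.7.4, explaining why procedure time should not change, says that "the final comparison of data recorded from the Standard EP recording system and the tested device will occur post procedure".

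**The concern.** A single site satisfies the rule, and nothing says how that site or its baseline window is found. In an open-label study compared after the procedure, both recordings exist when the measurement is made. A reader could comply fully with the SAP and still measure where ECGenius happens to look quiet.

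Matching the window across systems is good practice but does not cure this. A window picked because the ECGenius trace is clean gives an ECGenius value that is low by selection. The existing system's value in that window is only partly correlated with it and stays closer to its usual level. The paired difference then favours ECGenius even when the systems are equal. The absolute limits are more exposed, because no comparator shares the shift.

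Among the primary performance items, low-voltage recording is a count plus a physician's score, and shape and timing carry no hypothesis. Baseline noise is the only objective measurement with a comparative hypothesis, and it carries the improved-signal item.

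**Working it through.** **The plan's own figure.** The only design figure is the sample size in SAP 5.5: (30 + 20 + 40)/3 = 30, which reproduces. It does not involve noise. Protocol 7.1 states that no formal hypothesis was used to derive the sample size.

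**Inputs.** From the documents: 30 procedures, paired recordings, limits of 50 and 20 uV. Assumed, because the documents give no values: k candidate windows per procedure (2, 3, 5); correlation r between the two systems' noise in the same window (0.5, 0.8); normal noise with equal mean and SD on both systems; a paired t-test at one-sided 2.5%. Differences are in units of the within-procedure window SD.

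**Bias in the paired difference.** If the shared window is the one with the lowest ECGenius noise among k, the expected shift towards ECGenius is (1 − r) × |m_k|. Here m_k is the expected minimum of k standard normals: −0.56, −0.85 and −1.16 for k = 2, 3 and 5.
- r = 0.5: 0.5 × 0.56 = 0.28; 0.5 × 0.85 = 0.42; 0.5 × 1.16 = 0.58.
- r = 0.8: 0.2 × 0.56 = 0.11; 0.2 × 0.85 = 0.17; 0.2 × 1.16 = 0.23.

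The shift is zero only if k = 1 or r = 1.

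**Check of one entry.** For k = 2, r = 0.5, the variance of the minimum is 0.68. The variance of the paired difference is (1 − r)² × 0.68 + (1 − r²) = 0.25 × 0.68 + 0.75 = 0.92, so the SD is 0.96. The non-centrality is 0.28 × √30 / 0.96 = 1.6. Against a critical value of 2.045 (29 degrees of freedom), this gives about 34%, in line with simulation.

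**Simulated rate of a false finding that ECGenius noise is lower** (systems equal; repeat runs agree to within about two percentage points):

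| Selection on the ECGenius trace | r | k = 2 | k = 3 | k = 5 |
|---|---|---|---|---|
| Every procedure | 0.5 | 35% | 65% | 91% |
| Every procedure | 0.8 | 16% | 31% | 52% |
| A quarter of procedures | 0.5 | 6% | 8% | 11% |
| A quarter of procedures | 0.8 | 4% | 6% | 7% |
| None | either | about 2.5% | about 2.5% | about 2.5% |

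The first two rows also assume that the true difference between systems is the same in every procedure. If it varies between procedures with an SD equal to the window SD, the second row falls to about 7%, 11% and 18%.

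**Relation to non-inferiority.** The SAP states no margin. In this model a margin only shifts the difference by a constant. If ECGenius were truly worse by exactly the margin, the same t-test would falsely conclude non-inferiority at the tabulated rates.

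**Absolute limits.** Suppose the true means are 10% over each limit (55 and 22 uV) and the between-site coefficient of variation is 20% (assumed). Reporting the quieter of two sites gives 55 × (1 − 0.2 × 0.564) = 48.8 uV and 22 × (1 − 0.2 × 0.564) = 19.5 uV. Both limits then appear to be met.

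**The case against.** **Selection is read into silence.** Nothing says that sites are chosen after viewing traces, and Protocol 4.7.4 times the final comparison, not the choice of sites. This stands: the point is what the plan permits.

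**The noise reader is not the principal investigator on the text.** A reader might infer this from Protocol 4.5.1: "This evaluation will be done by the institution principal investigator for both signal and mapping if available". That sentence follows the 1-to-5 rating and refers to it. No reader is named for the noise measurement, so an unmasked investigator picking windows is not documented.

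**A benign reading exists.** The wording can mean a minimum of one site, with all low-voltage sites averaged. The SAP also asks to "Count number of low-voltage electrograms plotted in total", so the number available would be visible. If all eligible sites were averaged, the bias from choosing among sites would vanish. The text does not require this, however, and with low-voltage undefined and no window rule, the eligible pool and the stretch of baseline both stay open.

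**The rates belong to no planned test.** The SAP states non-inferiority without a margin, alpha or test, and Protocol 7.2 plans descriptive summaries. This stands for the percentages. The bias itself does not depend on a test, since it moves the reported means.

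**The upper figures are a worst case.** This also stands. They need the quietest window in all 30 procedures, and partial selection brings the rates close to nominal.

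**Conclusion.** The concern holds as a gap in the measurement rule. SAP 5.6 can be followed to the letter with one site and window chosen in view of the noise traces. Any choice that follows the ECGenius trace biases the absolute and comparative noise results in its favour, with or without a shared window.

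The size cannot be stated from the documents, which give no noise SD, between-system correlation or number of candidate sites. Under the assumptions shown, it runs from near nominal to severe.

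A reader might infer that the trial will favour ECGenius, or that its error rate is as high as 91%. The documents support neither. No passage describes selective reading, and that figure combines the most extreme assumptions shown with a test the SAP does not contain. The change is worth making because it is cheap and removes the question before data exist.

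**What to change.** In SAP 5.6, replace the present site rule with the following:
- Measure all sites that meet a low-voltage amplitude cut-off fixed before the first subject. If there are too many, take a fixed number in time order or at random.
- List the sites before any noise is measured and without sight of the noise traces.
- Do not base eligibility on one system's amplitude alone. That reading contains the system's own noise, so it would select on that system. Requiring the cut-off on both systems is one solution.
- On both systems use the same electrodes, the same fixed-length baseline window by clock time, and the same filter settings.
- Exclude a window only if it is unusable under a pre-stated rule applied to both systems.
- Average within procedure and analyse one paired difference per procedure, separately for unipolar and bipolar recordings.

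If feasible, let an automated routine or a reader masked to the system take the measurement.

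The cost is SAP wording, slightly more reading time and less reader discretion. No extra subjects or procedures are needed, and a genuine noise advantage could not then be put down to the choice of site.

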1.3 RATIONALE FOR THIS CLINICAL INVESTIGATION

Electrograms and their interpretation are a key tool for electrophysiologists to target ablation sites and are acquired from electrodes on intracardiac diagnostic catheters and surface Electrocardiograms (ECGs). Besides the dominant noise contributor of 50/60Hz from the main power line, there are noise contributors from stimulation, ablation, and defibrillation artifacts that disturb the clear view of electrophysiological signals. Stimulation artifacts today are a result of (poor) software filter design, whereas ablation artifacts are mostly a hardware problem from the high energy exposure on the ablation tip electrode that is also used for measurements.

Baseline noise peak-to-peak levels below 15 μ V in bipolar recordings and below 30 μ V in unipolar recordings would be considered best-in-class. Bipolar recordings between adjacent band electrodes are the most commonly used and practically they are often “derived bipolar”. This means they are individual signals first amplified against a different but common reference, and then subtracted from each other. Unipolar recordings are important for advanced algorithms, such as 3D mapping

and rotor mapping for atrial fibrillation. The unipolar reference is most often Wilson Central Terminal (WCT), but it can also be a distant intracardiac electrode.

Electrograms are usually sampled at 1 to 2kHz, and bandpass filtered at 30 to 500Hz for bipolar and 0.5 to 300Hz for unipolar recordings. 64 to 160 channels are the typical capacity of recording systems today.

In the operating room, other devices and technologies are present: 3D mapping (triangulation of catheter tip position with impedance- and magnetic technology, <0.2 gauss), fluoroscopy/X-ray, Radiofrequency (RF) generator, cryo gas station, stimulator, saline coolant pump for ablation catheter RF-tip irrigation, hemodynamics, magnetic catheter steering (0.08T).

It is not unusual to defibrillate the patient to cardiovert them from an arrhythmia. It is not unusual that patients have implanted cardioverter-defibrillators (ICDs).

It is CathVision's goal to develop a new electrophysiology recording system with improved signal quality particularly of unipolar recordings, with fast pacing and defibrillation recovery times, and with minimal or reduced RF ablation artifacts. The reduction in noise and artifacts will allow for better diagnosis and delivery of advanced ablation therapy in arrhythmia patients.

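### SAP 5.6 judges improved signal quality by unexplained noise cut-offs (50/20 µV) that are looser than Protocol 1.3's best-in-class levels (30/15 µV), and no benchmark in that row can show improvement over the standard signal

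*SAP*

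**What the plan says.** Protocol 4.5.1 lists as part of the primary outcome: "To assess the improved signal (better signal to noise ratio) compared with the standard signal". The protocol synopsis and SAP 5.4 carry the same item.

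The third row of the table in SAP 5.6 turns this into numbers. Its endpoint is labelled "Assessing the improved signal quality (baseline noise level peak-to-peak", and it has three benchmarks:

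- "Hypothesis is below 50uV unipolar baseline noise peak-to-peak"
- "Hypothesis is below 20uV bipolar baseline noise peak-to-peak"
- non-inferiority to the existing EP recording system, with no margin, test or confidence level.

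Protocol 1.3 gives figures for a measure of the same name. It begins "Baseline noise peak-to-peak levels below 15 μ V in bipolar recordings" and continues "below 30 μ V in unipolar recordings would be considered best-in-class". The same section gives the development goal as a system with "improved signal quality particularly of unipolar recordings".

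**The concern.** The row carries the word *improved*, but its absolute limits are looser than the only other noise levels in the documents. The larger gap is on the unipolar side, which is where Protocol 1.3 places the emphasis. Neither document gives a source or reason for 50/20 µV.

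What is at stake is the wording of the conclusion. A report could say that the improved-signal hypotheses were met when the result shows only that noise stayed under a limit of unknown origin and that the device was not unacceptably worse than the comparator. A reader could not tell from that statement whether the signal was better than the standard signal, or how it stood against the levels in the trial's own rationale.

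**Working it through.** **Inputs.** From SAP 5.6: limits of 50 µV (unipolar) and 20 µV (bipolar). From Protocol 1.3: best-in-class levels of 30 µV and 15 µV. All four are peak-to-peak baseline noise in µV. The SAP gives no derivation for 50/20 µV, so there is no planned figure to reproduce.

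**Step 1: size of the gap.** Relative gap = (SAP limit − protocol level) / protocol level.

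| | SAP limit | Protocol level | Difference | Ratio | Relative gap |
|---|---|---|---|---|---|
| Unipolar | 50 | 30 | 50 − 30 = 20 µV | 50/30 = 1.67 | 20/30 = 67% |
| Bipolar | 20 | 15 | 20 − 15 = 5 µV | 20/15 = 1.33 | 5/15 = 33% |

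**Step 2: what the absolute limits let through.** A device at 40 µV unipolar and 18 µV bipolar (illustrative) meets both SAP limits, since 40 < 50 and 18 < 20. It misses both protocol levels, since 40 > 30 and 18 > 15. Devices at 31/16 and 49/19 give the same result.

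**Step 3: the third benchmark.** The documents give neither the comparator's noise nor a margin, so both are assumed here. The rule applied to point estimates is: device noise ≤ comparator noise × (1 + margin), for unipolar and bipolar alike. Margins tried were 0%, 10%, 20% and 50%.

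| Device | Comparator | Result |
|---|---|---|
| 40/18 | 25/12 | fails at every margin tried (at 50%, the unipolar limit is 25 × 1.5 = 37.5 < 40) |
| 40/18 | 30/15 | fails at 0–20% (at 20%, 30 × 1.2 = 36 < 40); passes at 50% (45 and 22.5) |
| 40/18 | 40/18 | passes at every margin, including 0% |
| 49/19 | 40/18 | fails at 0–20% (at 20%, 40 × 1.2 = 48 < 49); passes at 50% (60 and 27) |

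Whether a device in the gap meets the whole row therefore depends on two quantities that the documents do not give.

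**Step 4: can meeting the row show improvement?** No. In the third line of the table the device meets all three benchmarks with exactly the comparator's noise. In the fourth, at a 50% margin, it meets all three while noisier on both channels (49 against 40, 19 against 18).

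**Step 5: would 30/15 µV do better?** Not for this purpose. A device at 28 µV unipolar beside a comparator at 20 µV is below 30 µV and yet noisier. A device at 40 µV beside a comparator at 60 µV is above 30 µV and yet quieter. No absolute limit answers a relative question.

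**The case against.** Three stronger readings are tempting, and the documents support none of them.

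*The SAP contradicts the protocol.* It does not. Protocol 1.3 is a background section that says which levels would count as best-in-class. It sets no acceptance criterion, and a pass level below best-in-class is not inconsistent with that description. Nor does the protocol say how its figures were obtained (bench or patient, filter settings, recording site), whereas the SAP specifies sites with low-voltage electrograms. The percentages in Step 1 are correct arithmetic, but they compare like with like only if the conditions match.

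*The SAP should adopt 30/15 µV as the test of improvement.* Step 5 shows why this would not work. Protocol 1.3 also cites no source for 30/15 µV, so the change would swap one unsourced pair for another.

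*Any device between the two sets of limits passes.* This is certain only for the two absolute limits. The whole row also includes non-inferiority, and the SAP averages over sites within a procedure but states no rule for passing across procedures.

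It can also be said that the consequence is modest. Protocol 7.1 used no formal hypothesis for sample size, Protocol 7.2 plans descriptive summaries from which a reader could make the comparison, and Protocol 4.2 keeps the device out of clinical decisions. That limits the weight of the point but does not remove it. SAP 5.6 presents these figures as hypotheses and benchmarks under a label of improvement, so results will be read against them.

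**Conclusion.** The concern holds as an unexplained mismatch together with a benchmark that does not fit its label. The SAP limits exceed the Protocol 1.3 levels by 20 µV (67%) unipolar and 5 µV (33%) bipolar, with no reason given. Those sizes assume that the two sets of figures were measured under comparable conditions, which the documents do not establish.

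The conclusion that matters most does not depend on that assumption. None of the row's three benchmarks, met singly or together, can show that the signal is better than the standard signal. Whether 50/20 µV would be an improvement on the existing system cannot be determined, because its noise level is not given.

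**What to change.** In the third row of the SAP 5.6 table:

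1. Label 50/20 µV a minimum acceptability limit that supports no claim of improvement, and state its rationale.
2. Base any statement of improvement only on the within-procedure paired difference in baseline noise between the two systems, separately for unipolar and bipolar recordings, as an estimate with a confidence interval. Parallel recording (Protocol 4.2) makes the pairing possible. The documents give no standard deviation, so the width of that interval cannot be predicted.
3. For both systems, report the number and percentage of procedures below 50/20 µV and below the 30/15 µV reference levels of Protocol 1.3.

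The non-inferiority comparison already needs noise measured on both systems, so no new subjects, visits or measurements are required. The cost is SAP wording, the paired estimate and one extra summary line. The downside for the sponsor is small: meeting 50/20 µV can no longer be presented as improved signal quality. The change should be made before the data are analysed, so that the limits are not chosen after the results are known.
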